#### **KPT-9274 Dose Escalation Levels**

Cohort	KPT-9274	
	Days 1, 3, 5, 8, 10, 12, 15, 17, 19, 22, 24, 26 in a 28-day cycle	
0 (de-escalation, if needed)		20 mg
1 (starting cohort)		30 mg
2		40 mg
3		60 mg
4		80 mg
5		100 mg

## **2.2. Replacement Policy**

Patients who complete the first cycle of therapy will not be replaced during the Escalation Phase of the study. However, if a patient is considered as non-evaluable for DLT (i.e., did not complete the first cycle of therapy or the minimum number of doses of KPT-9274 and did not experience a DLT), enrollment of a new patient to the current cohort will be considered if there is less than the required number of evaluable patients.

During the Dose Expansion Phase, patients who have not completed 1 cycle will be replaced unless they were discontinued from the study due to a drug-related toxicity, PD, or death.

## **2.3. Treatment Duration**

Treatment cycles are 28 days long. A patient may continue to receive KPT-9274 until that patient experiences PD, withdraws consent, is lost to follow-up, experiences intolerable toxicity which precludes further treatment with KPT-9274, or treatment is discontinued at the discretion of the Investigator.

### 3. STUDY POPULATION SELECTION

#### 3.1. Study Population

This study will enroll adult patients with relapsed or refractory AML for whom standard therapeutic options considered useful by the investigator have been exhausted, and meet all of the inclusion criteria and none of the exclusion criteria.

#### 3.2. Eligibility

##### 3.2.1. Inclusion Criteria

Patients must meet all of the following inclusion criteria to be eligible to enroll in this study.

1. Written informed consent obtained prior to any screening procedures
2. Age  $\geq 18$  years.
3. Patients with WHO-confirmed non-APL AML who have not responded to or relapsed after at least one prior therapy and for whom no standard therapy that may provide clinical benefit is available.
4. Eastern Cooperative Oncology Group (ECOG) performance status of  $\leq 2$ .
5. Adequate hepatic function:
  - Total bilirubin  $< 1.5$  times the upper limit of normal (ULN) (except patients with Gilbert's syndrome [hereditary indirect hyperbilirubinemia], subjects with Gilbert's syndrome, total bilirubin needs to be  $\leq 4$  x ULN).
  - Aspartate aminotransferase (AST) and alanine aminotransferase (ALT)  $\leq 2.5$  times ULN (except patients with known liver involvement of their AML who must have AST and ALT  $\leq 5.0$  times ULN).
6. Adequate renal function: estimated creatinine clearance of  $\geq 60$  mL/min, calculated using CKD-EPI Creatinine Equation (2021). <https://www.kidney.org/content/ckd-epi-creatinine-equation-2021>.
7. Female patients of child-bearing potential must agree to use dual methods of contraception (including one highly effective and one effective method of contraception) and have a negative serum pregnancy test at Screening. For both male and female patients, effective methods of contraception must be used throughout the study and for 3 months following the last dose.
  - a. Fertile female patients must agree to refrain from egg donation from first dose until at least 3 months following the last dose of KPT-9724.
  - b. Women should not breastfeed during treatment with KPT-9724 and for 2 weeks after the last dose.
  - c. Male patients must use 2 highly effective methods of contraception if sexually active with a female of child-bearing potential, during treatment with KPT-9724, during a period of 2 weeks (5 half-lives) after the last dose of KPT-9724 plus a period of 3 months. (for 3.5 months after their last dose of KPT-9724). Fertile male patients must agree to refrain from sperm donation from first dose until at least 3.5 months following the last dose of KPT-9724.

### **3.2.2. Exclusion Criteria**

Patients meeting any of the following exclusion criteria are not eligible to enroll in this study.

1. Female patients who are pregnant or lactating.
2. Radiation, chemotherapy, immunotherapy or any other anticancer therapy, including investigational anti-cancer therapy  $\leq$  2 weeks prior to C1D1. Hydroxyurea is not considered an anti-cancer therapy.
3. Patients who have not recovered or stabilized (Grade 1 or to their baseline for non-hematologic toxicities) from toxicities related to their previous treatment, except for alopecia.
4. White blood cell count  $\geq 25 \times 10^9/L$  (hydroxyurea or leukapheresis permitted to reduce to below the exclusion criteria threshold and allow eligibility)
5. Patients with known active central nervous system (CNS) disease
6. Clinically significant severe heart disease
7. Active clinically significant infection. Use of prophylactic antibiotics, antivirals or antifungals are permitted.
8. Known, active hepatitis A, B, or C infection; or known to be positive for HCV RNA or HBsAg (HBV surface antigen). Testing is not required.
9. Patients with significantly diseased or obstructed gastrointestinal tract or uncontrolled vomiting or diarrhea that could interfere with the absorption of KPT-9274.
10. Serious psychiatric or medical conditions that, in the opinion of the Investigator, could interfere with treatment, compliance, or the ability to give consent.

### **3.3. Screening and Registration**

The Screening period starts once a patient has provided written informed consent to participate in the study and ends on the day of study entry (C1D1).

Patient eligibility (inclusion/exclusion criteria) will be reviewed for each patient participating in the study by the investigator before the patient receives study treatment on C1D1.

Upon signing consent, each patient will be assigned a unique patient number and will keep this number for the duration of the study.

#### **3.3.1. Screen Failures**

Patients who sign an informed consent but fail to start on treatment for any reason will be considered a screen failure. Date of consent and reason for ineligibility will be entered into the clinical database. No other data will be entered into the clinical database for patients who are screen failures, unless those patients experience serious adverse event (SAE) related to study procedures during the Screening Phase.

## 4. DISCONTINUATION CRITERIA

### 4.1. Early Termination of the Study

This study may be discontinued at the discretion of the Sponsor for any reason. This could occur due to concerns related to safety, tolerability or efficacy of KPT-9274.

### 4.2. Discontinuation of Study Treatment and/or Withdrawal of Patients from the Study

The Investigator may remove a patient from study treatment for any of the following reasons:

- Unacceptable AEs or toxicity that cannot be managed by supportive care
- Any medically appropriate reason (e.g., clinical progression) or significant protocol violation, in the opinion of the Investigator

The Investigator must remove a patient from study treatment for any of the following reasons:

- Disease progression per response criteria
- Patient withdraws consent to continue study treatment
- Pregnancy

Patients who are removed from study treatment by the Investigator are not permitted to restart study treatment.

Patients may discontinue study treatment for any reason. Patients who choose to discontinue study treatment will be encouraged to continue in the study so that follow-up information on disease progression and survival status may be obtained. Patients may elect to withdraw consent and decline further participation in the study at any time.

The reason for the patient's discontinuation of study treatment/withdrawal from the study must be recorded on the eCRF.

All patients will be followed until PD, withdrawal of consent, occurrence of any withdrawal criteria, intolerable toxicity precluding further treatment with study treatment, death or lost to follow up.

## 5. STUDY TREATMENTS

### 5.1. Treatments Administered

#### 5.1.1. Study Treatments

KPT-9274 is an orally bioavailable small molecule prepared in a tablet solid dosage form for oral administration.

KPT-9274 tablets are designed for immediate-release oral administration and will be supplied in high-density polyethylene (HDPE) bottles with induction seals and polypropylene caps. KPT-9274 tablets will be film coated for ease of handling and provided in tablet strengths of 5 mg and 20 mg. KPT-9274 will be supplied by Karyopharm. Additional details on KPT-9274 are provided in the IB. The investigational treatments will be administered as a flat dose and not by body weight or body surface area.

### 5.2. Study Treatment Dose Schedules and Administration

#### 5.2.1. Labeling

All labels will include conditions for storage, lot number, and other information required by the Food and Drug Administration (FDA), International Council for Harmonisation (ICH), and/or Annex 13, and all local regulations for investigational medications.

#### 5.2.2. Dispensing Directions

The Investigator or responsible site personnel must instruct the patient or caregiver to take the study treatment(s) as per protocol. Study treatment(s) will be dispensed to the patient by authorized site personnel only.

#### 5.2.3. Dosing Information

Patients will receive oral KPT-9274 three times a week every other day (Days 1, 3, 5, 8, 10, 12, 15, 17, 19, 22, 24, and 26) during each 28-day cycle.

#### 5.2.4. Dosing Instructions for Patients

Study medications will be dosed according to the schedules provided in [Table 4](#). Patients will be provided with a take home diary to complete; the patient diary will be reviewed prior to the next cycle.

Oral KPT-9274 should be given with food, or within 30 minutes after the patient has eaten, together with 240-355 mL (8-12 ounces) of fluids.

KPT-9274 tablets should be swallowed whole (not crushed).

#### 5.2.5. Dose Schedules for Evaluation During the Dose Escalation Phase

The dose schedule for evaluation during the Dose Escalation Phase is presented in [Table 8](#).

**Table 5 KPT-9274 Dose Escalation Levels*****KPT-9274 Dose Escalation Levels***

Cohort	KPT-9274
	Days 1, 3, 5, 8, 10, 12, 15, 17, 19, 22, 24, 26 in a 28-day cycle
0 (de-escalation, if needed)	20 mg
1 (starting cohort)	30 mg
2	40 mg
3	60 mg
4	80 mg
5	100 mg

Three patients will be enrolled in each cohort, if 1 of 3 patients in a cohort experiences a DLT, the number of patients in that cohort will be expanded to 6 patients. A maximum of 6 patients will be enrolled per cohort. The MTD is defined as the highest dose at which  $\leq 1$  patients out of a maximum potential cohort of 6 experiences a DLT.

### 5.2.6. Dose Escalation Guidelines

#### 5.2.6.1. Dose Escalation Procedures

For the purposes of dose escalation decisions, a standard 3+3 dose escalation design will be used.

The initial cohort, Cohort 1, will consist of 3 enrolled patients who will be treated at 30 mg. If these patients do not experience a DLT during Cycle 1, the KPT-9274 dose will be escalated to 40 mg for another group of 3 patients (Cohort 2). If the MTD is exceeded at cohort 1, de-escalation to cohort 0 (20 mg) will occur. If the MTD is not exceeded in cohort 1, dose escalation will continue based on a standard 3+3 design at the dose levels specified in

Table 8.

A RP2D equal to or less than the MTD will be declared at the conclusion of the dose escalation, and potentially used for the Dose Expansion Phase. The RP2D will be based on an evaluation of any and all pharmacokinetic, pharmacodynamic and safety data, including an evaluation of SAEs that occur after the end of the DLT window to ensure the tolerability of the RP2D. The MTD is defined as the highest dose at which  $\leq 1$  patient experiences a DLT in Cycle 1.

Patients must complete a minimum of 1 cycle of treatment, defined as receiving  $\geq 75\%$  of KPT-9274 doses during Cycle 1 (e.g.,  $\geq 9$  of 12 doses in the 3 doses/week schedule), or have a DLT within the first cycle of treatment to be evaluable for dose escalation decisions. Dose escalation decisions will occur when the cohort of patients has met these criteria.

Dose escalation will be conducted as follows:

- If 0 of 3 patients experiences a DLT, escalate to next higher dose cohort.

- If 1 of 3 patients experiences a DLT, that cohort will be expanded to 6 patients. If 1 of 6 patients experiences a DLT, escalate to the next higher dose cohort;
- If  $\geq 2$  of 3 or  $\geq 2$  of 6 patients experience a DLT, MTD is exceeded. If the MTD is exceeded, the patients will be de-escalated to the next lower dose level (the MTD).

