### **5.2.6.2. Dose-Limiting Toxicity**

A DLT will be defined as an AE or abnormal laboratory value that occurs within the first 28 days of treatment with KPT-9274, except for those that are clearly and incontrovertibly due to underlying disease, disease progression, or extraneous causes, and meets any of the criteria for defining dose-limiting toxicities as described in the table below. The CTCAE, Version 5.0 will be used for grading. In addition,  $> 3$  missed (consecutive or nonconsecutive) doses of KPT-9274 in the first 28 days due to a drug related toxicity will be considered to be a DLT.

Other events may occur which do not meet the definition of a DLT but are of concern to the Investigators may be considered to be DLTs.

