**Table 7 KPT-9274 Dose Modification and Supportive Care Guidelines**

Toxicity and Intensity	Dose Modification
Non-hematologic Toxicity	
Grade 1	Maintain dose. Consider instituting supportive care medications per institutional guidelines.
Grade 2	Institute supportive care medications per institutional guidelines.  If modifications are desired, guidelines for AEs $\geq$ Grade 3 should be followed. At the Investigator's discretion, patients may continue on KPT-9274 uninterrupted at their current dose.
$\geq$ Grade 3	Optimal supportive care medications according to institutional guidelines should be instituted.  Hold KPT-9274 until the event resolves to $\leq$ Grade 1 or baseline (as appropriate): 
 
First occurrence of <math>\geq</math> Grade 3:               
 
If supportive care results in the AE improving to Grade <math>\leq</math> 1 or baseline within 3 days, restart KPT-9274 at the current dose.
 
If the improvement to Grade <math>\leq</math> 1 or baseline takes longer than 3 days, KPT-9274 should be resumed at 25% of the dose.
 
 
 
Second or greater occurrence of <math>\geq</math> Grade 3, restart KPT-9274 at 50% of the dose upon improvement to Grade <math>\leq</math> 1 or baseline irrespective of duration.
 
 **If the toxicity does not resolve to $\leq$ Grade 1 or baseline within 28 days, study treatment will be discontinued permanently.
Hematological Toxicity for AML Patients	
AML patients typically have abnormal peripheral blood counts at diagnosis; myelosuppression is an expected event during the course of any therapy. Therefore, no dose adjustments or treatment interruption for hematological toxicity will occur during the first cycle or at any cycle in the presence of residual AML. Dose adjustments and/or treatment interruptions for hematological toxicity will be considered after the first cycle, in the absence of residual disease, according to the following guidelines:	

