#### 8.3.3. DLT Evaluable Population

All patients who complete a minimum of 1 cycle of treatment, defined as having received  $\geq 75\%$  of KPT-9274 doses during Cycle 1 (e.g.,  $\geq 9$  of 12 doses in the 3 doses/week schedule), or who have a DLT within the first cycle of treatment, will be included in the DLT evaluable population.

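### DLT evaluability counts Cycle 1 doses whatever their size, while the plan contradicts itself on whether a dose can be cut inside the DLT window

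*Combined protocol and SAP*

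**What the plan says.** **Evaluability.** Section 5.2.6.1 asks for at least 75% "of KPT-9274 doses during Cycle 1", with the example of at least 9 "of 12 doses in the 3 doses/week schedule", or a DLT. The synopsis and Section 2.1 repeat this. The analysis population in Section 8.3.3 uses the same test: "All patients who complete a minimum of 1 cycle of treatment", with completion defined by the 75% count, "or who have a DLT within the first cycle of treatment, will be included in the DLT evaluable population". None of these places sets a condition on the size of the dose.

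**Missed doses.** Section 5.2.6.2, like the synopsis, makes it a DLT to have more than 3 "missed (consecutive or nonconsecutive) doses of KPT-9274 in the first 28 days due to a drug related toxicity". No criterion in Table 6 mentions a reduced dose.

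**Reductions, Table 7** (cited in the text as Table 10). For a first non-hematologic event of Grade 3 or higher that takes more than 3 days to improve to Grade 1 or baseline, "KPT-9274 should be resumed at 25% of the dose". Grade 2 events may take the same route: "If modifications are desired, guidelines for AEs" of Grade 3 or higher apply. These rows name no cycle. The hematologic rows of the same table exclude the first cycle outright.

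**Reductions, Section 5.2.8.** The text that introduces the table permits dose adjustments once morphologic remission is reached. Its own sequence (same dose first, 25% on recurrence) is written for the time after the DLT period. A patient with a DLT in Cycle 1 of the escalation phase must stop KPT-9274.

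**The concern.** The MTD is the primary objective, and each escalation decision rests on 3 to 6 patients. A patient who enters the count without a DLT is read as evidence that the cohort dose is tolerable for 28 days. If that patient spent most of the cycle on a quarter of the dose because of drug toxicity, the evidence concerns a much lower exposure, but the count does not show it. The error runs one way: reduced exposure can prevent a DLT but does not remove the patient from the denominator. The next cohort could then be opened on weaker evidence than the 3+3 rule assumes.

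**Working it through.** **1. The plan's own figure.** There are 12 dosing days in Cycle 1 (Section 5.2.3): 1, 3, 5, 8, 10, 12, 15, 17, 19, 22, 24, 26. Then 0.75 × 12 = 9, as stated. The missed-dose rule fits it: 12 − 3 = 9, so more than 3 missed means at most 8 taken. Both rules are counts.

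**2. Can a Cycle 1 cut occur without a DLT?** Table 6 times how long AST/ALT stays at Grade 3 (7 days or more is a DLT). Table 7 times recovery to Grade 1 or baseline (more than 3 days leads to 25%). Grade 3 ALT that recovers in 4 to 6 days, without Grade 2 direct hyperbilirubinemia, is therefore not a DLT but does meet the Table 7 condition. The same can hold for Grade 3 neutropenic fever, for Grade 3 nausea, vomiting or diarrhea controlled within 72 hours (without hospitalization, parenteral nutrition or tube feeding) but slow to reach Grade 1, and, optionally, for Grade 2 events.

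**3. Exposure of such a patient.** Exposure = (full doses + 0.25 × reduced doses) / 12.

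| Case | Full | Missed | At 25% | Taken | Exposure |
|---|---|---|---|---|---|
| Onset Day 2, 4–6 days | 1 | 2 | 9 | 10 | 3.25/12 = 27.1% |
| Onset Day 4, 5–6 days | 2 | 2 | 8 | 10 | 4/12 = 33.3% |
| Onset Day 9, 4–6 days | 4 | 2 | 6 | 10 | 5.5/12 = 45.8% |
| Lowest with at least one full dose and 3 missed | 1 | 3 | 8 | 9 | 3/12 = 25.0% |

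All four are evaluable with no missed-dose DLT. Later onset gives higher exposure. In the 80 mg cohort the Day 2 patient receives 80 + 9 × 20 = 260 mg, less than a full cycle in the 30 mg starting cohort (12 × 30 = 360 mg), yet counts toward opening 100 mg.

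**4. Sensitivity to the 25% figure.** Table 7 also contains a 50% restart, for a second or later event. With 0.50 in place of 0.25, the lowest case is (1 + 8 × 0.50)/12 = 41.7% and the Day 9 case is (4 + 6 × 0.50)/12 = 58.3%. Both are still below 75%.

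**5. Effect on escalation (assumed inputs).** Under Section 5.2.6.1 a cohort escalates on 0/3, or on 1/3 followed by 0/3. At DLT rate p, P(escalate) = (1 − p)³ + 3p(1 − p)² × (1 − p)³. Suppose the cut averts a fraction f of would-be DLTs, so that p becomes p(1 − f). Neither p nor f is given in the documents.

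| True p | f = 0 | f = 0.10 | f = 0.20 | f = 1/3 |
|---|---|---|---|---|
| 0.30 | 0.494 | 0.557 | 0.622 | 0.709 |
| 0.40 | 0.309 | 0.378 | 0.454 | 0.564 |

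For example, at p = 0.30 and f = 0.10 the rate is 0.27: 0.73³ = 0.389, plus 3 × 0.27 × 0.73² × 0.389 = 0.168, total 0.557.

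**6. If only cohort-level doses counted toward the 9.** Every case in step 3 has 1 to 4 full doses and would not be evaluable. An evaluable patient without a DLT would have received at least 9/12 = 75% of planned exposure.

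**The case against.** The strongest reply is that Section 5.2.8 governs Table 7. It allows adjustments only after morphologic remission, and Section 6.3.2 starts response assessment with the Day 28 marrow, when the last Cycle 1 dose falls on Day 26. On that reading Cycle 1 cuts are largely ruled out. A reader might infer from Table 7 alone that the Cycle 1 cut is an established part of the plan. The documents do not support that; they conflict.

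The conflict does not close the gap, however. Holds in Cycle 1 are foreseen: Section 5.2.6.2 counts them, and before remission Section 5.2.8 bars holds only for toxicity not attributable to KPT-9274. Its same-dose restart begins after the DLT period. For a patient held inside the window, the only explicit restart instruction is Table 7.

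Other safeguards are partial. Most other clinically significant non-hematologic events of Grade 3 or higher are already DLTs, which keeps the path narrow. Investigators may call further events of concern DLTs, but need not. The RP2D may be set below the MTD using all PK, PD and safety data. Dose modifications are discussed at regular meetings and reported to the DSMC (Section 9.8.2). None of these changes who counts toward the MTD.

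The 25% figure is itself unsettled. Table 7 gives 25% after a first slow event but 50% after a second, and 25% of 30 mg is 7.5 mg, which whole 5 mg and 20 mg tablets cannot make up. This affects the size of the exposure loss, not the fact that the rules ignore dose size.

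**Conclusion.** The point stands in a conditional form. The evaluability and missed-dose rules count administrations only; that is plain from the text. If a site follows the non-hematologic rows of Table 7 in Cycle 1, a patient with a non-DLT event can be scored as tolerating the cohort dose on about 25% to 46% of planned exposure in the cases worked here, and the bias in escalation is upward.

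Two stronger conclusions should be resisted. One is that the MTD will be overstated by a known amount. How often such patients would occur cannot be derived from the documents, so the rise from 0.494 to between 0.557 and 0.709 (true rate 0.30, f from 0.10 to one third) is an illustration. The other is that treating reduced doses as missed doses would be a pure counting change. It would create DLTs, and Section 5.2.8 turns a Cycle 1 DLT into mandatory discontinuation.

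**What to change.** 1. Reconcile Section 5.2.8 with the non-hematologic rows of Table 7 on whether dose reductions can occur within the DLT window, including the differing restart levels. Which rule is clinically right is for the sponsor to decide.
2. In the synopsis and Sections 2.1, 5.2.6.1 and 8.3.3, count only doses given at the assigned cohort dose toward the 9 of 12. A patient reduced early without a DLT is then non-evaluable and falls under the replacement policy in Section 2.2. If step 1 excludes Cycle 1 reductions, this wording does no harm.
3. State, identically in the synopsis and Section 5.2.6.2, how doses reduced for toxicity relate to the rule under which more than 3 missed "doses of KPT-9274 in the first 28 days due to a drug related toxicity will be considered to be a DLT". The sponsor should weigh the discontinuation that follows from a Cycle 1 DLT. No DLT rule is proposed here.
4. List separately, by cohort, patients who are non-evaluable because of a toxicity-driven reduction, and show them at each escalation decision. Replacing them without this would discard evidence about tolerability.

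The cost is wording in a few places. Dosing deviations and missed doses already go into the eCRF, and compliance is checked by diary and tablet count (Section 5.6). Expect an occasional replacement patient and slightly slower escalation.

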## **1.4. Objectives**

### **1.4.1. Primary Objective**

- To assess the maximum tolerated dose (MTD)

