### 8.2. Determination of Sample Size

#### 8.2.1. Sample size

The sample size for the Dose Escalation Phase is based on a standard 3+3 design for the purpose of determining the RP2D and MTD. Each cohort will consist of 3 or 6 patients per cohort.

For the Dose Expansion Phase, up to 10 additional patients may be enrolled at the RP2D for KPT-9274

Assuming that 4 dose levels of KPT-9274 are evaluated during the Dose Escalation Phase and up to 10 additional patients are enrolled in the Dose Expansion Phase, the total combined enrollment is estimated to be at most 34 patients.

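### The level below an exceeded dose is named the MTD without first being filled to 6 patients, so the primary objective would usually rest on 3; the action at an early second DLT is also unstated

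*Combined protocol and SAP*

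**What the plan says.** The primary objective is "To assess the maximum tolerated dose (MTD") (Section 1.4.1). Section 5.2.6.1 states that "a standard 3+3 dose escalation design will be used", without defining the term further, and then gives the rules:

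- "If 0 of 3 patients experiences a DLT, escalate to next higher dose cohort". The cleared level keeps 3 patients.
- "If 1 of 3 patients experiences a DLT, that cohort will be expanded to 6 patients". With 1 DLT in 6, escalation continues.
- Two or more DLTs of 3, or of 6, mean that the MTD is exceeded. Then: "If the MTD is exceeded, the patients will be de-escalated to the next lower dose level (the MTD").

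The synopsis and Section 5.2.5 define the MTD as the highest dose with at most 1 DLT and use 6 only as the largest size a cohort may reach. Section 8.2.1 says "Each cohort will consist of 3 or 6 patients per cohort". Section 5.2.6.1 takes escalation decisions once the cohort is evaluable, meaning at least 75% of Cycle 1 doses received or a DLT.

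**The concern.** Six patients are reached only through a DLT among the first three. A level that cleared on 0 of 3 is left at 3, and if the next level is exceeded it becomes the MTD with no further data. That dose answers the primary objective and is the ceiling for the RP2D, and so for any expansion. At the bottom of the range the label precedes all data: if 30 mg is exceeded, the literal wording makes 20 mg the MTD before anyone has been treated there.

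The second matter is smaller. After 1 DLT in 3 the cohort grows to 6, while the exceedance rule is worded for complete cohorts of 3 or 6. If the second DLT falls at patient 4 or 5, the outcome of the cohort is settled, but the text does not say whether the remaining places may still be filled.

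**Working it through.** **Inputs.** The decision rules are those of Section 5.2.6.1. The cap of 6 per cohort is in Section 5.2.5; the maximum of 30 in escalation and 10 in expansion is in the synopsis. The true DLT rate p at each dose is not given: Section 1.2.1 reports 3 DLTs in the completed study without denominators by dose. So p is left free first, and curves are assumed only afterwards. DLTs are taken as independent between patients.

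**1. The plan's own sizes.** 4 levels × 6 + 10 = 34 (Section 8.2.1) and 5 × 6 + 10 = 40 (synopsis). Both reproduce, and both already budget 6 patients at every level.

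**2. How often a cleared level holds only 3 patients.**

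- Cleared on 3 patients: (1−p)³.
- Cleared on 6 patients: 3p(1−p)² × (1−p)³.
- Share holding 3: 1 / [1 + 3p(1−p)²].

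This is 80.5% at p = 0.10, 72.3% at 0.20, 69.4% at 0.30 and 72.7% at 0.50. The term 3p(1−p)² peaks at p = 1/3, where it equals 4/9, so the share is never below 1/(1 + 4/9) = 9/13 = 69.2%. Results at the next level do not depend on how the lower one cleared, so the same floor applies to MTDs named after exceedance above Cohort 1, on any curve.

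**3. What the data at the named level show.** The exact one-sided 95% upper limit for the DLT rate is 1 − 0.05^(1/3) = 63% for 0/3 and 1 − 0.05^(1/6) = 39% for 0/6. For 1/6 it is 58%. A level with a true rate of 1/3 shows 0/3 with probability (2/3)³ = 29.6%.

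**4. What filling to 6 would detect.** A level cleared on 0/3 then fails if at least 2 of the next 3 patients have a DLT: 3p²(1−p) + p³ = 2.8% at p = 0.10, 10.4% at 0.20, 25.9% at 1/3 and 35.2% at 0.40.

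**5. Whole trial, three assumed curves (simulation).** Arrows run from the rules as written to 6 patients required at the named level. The all-trials column counts 100 mg as the MTD when it clears.

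| Assumed DLT %, Cohorts 0-5 | MTD on 3 patients, exceedance above Cohort 1 | Named level has p > 1/3, all trials | Same, a level above 30 mg exceeded | Mean escalation size |
|---|---|---|---|---|
| 3, 5, 10, 20, 35, 50 | 76% | 25.0% → 20.4% | 22% → 18% | 14.5 → 17.0 |
| 5, 10, 20, 35, 45, 55 | 74% | 25.3% → 21.4% | 27% → 23% | 11.9 → 14.4 |
| 2, 3, 5, 10, 20, 35 | 78% | 24.7% → 19.7% | 0% → 0% | 16.6 → 19.1 |

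The gain over all trials is 4.6, 3.9 and 5.0 points; where the criticised sentence operates above 30 mg it is 4, 4 and 0. On the third curve only 100 mg has a rate above 1/3, so once 100 mg is exceeded the level named is necessarily below it. The mean size rises by 2.5 in each row.

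**6. Second DLT in an expanded cohort.** Given 1/3, and assuming patients enter singly with each outcome known before the next, the second DLT falls at patient 4 or 5 with probability 1 − (1−p)²: 51% at p = 0.30 and 75% at 0.50. The expected number entered afterwards is 2p + p(1−p): 0.60 + 0.21 = 0.81 and 1.00 + 0.25 = 1.25. If patients 4 to 6 enter together, it is zero.

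**The case against.** **Imprecision belongs to designs of this size.** The upper limit of 63% for 0/3 looks poor, but 1/6, which the amended rule would accept, still gives 58%. This stands. The fix makes the named level better tested; it does not make the estimate precise.

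**The benefit is modest and depends on invented curves.** This also stands. A reader might infer that the fall from about 25% to 20-21% measures the effect of the criticised sentence. It does not: it is taken over all trials, including those in which 100 mg clears and no level is exceeded. The like-for-like gain is 0-4 points.

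**Other provisions protect the dose carried forward.** Section 5.2.6.1 lets the RP2D sit below the MTD on all PK, PD and safety data. Up to 10 more patients may be treated at the RP2D (Section 5.2.7) and pooled with escalation patients at that dose (Section 8.1). This is partial mitigation: the expansion is optional, and no rule revises the MTD from it.

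**The accrual point is only a gap.** A reader might infer that the plan orders enrolment up to 6 after a second DLT. It does not: two or more of 6 is already certain at that moment, and a site could reasonably stop. Ongoing safety review (Section 8.6), discretion to end the study (Section 4.1) and regular discussion of toxicity (Section 9.8.2) also apply. None of these is an accrual rule for the cohort, so the silence remains.

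**Conclusion.** The point holds in two parts of unequal weight. The main one is explicit in the text: a level cleared on 0 of 3 can be declared the MTD with no further patients. That this is the usual case needs no assumed curve, since the share cannot fall below 69%; it is 74-78% under the three curves used. The reduction in the chance of naming a level with a true rate above 1/3 does depend on the curves.

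The second part is an omission about accrual. The 0.81-1.25 patients entered after a second DLT, for p from 0.30 to 0.50, is an upper bound on what a stated rule could avoid.

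Two further inferences are not supported. The totals of 34 and 40 are not in error here; they differ only in the number of levels assumed. Nor can the first expansion patients supply the missing 3 at no cost: expansion follows completed escalation at an RP2D no higher than a declared MTD, so it could not open while the MTD was pending, and it has its own replacement rule (Section 2.2).

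**What to change.** Reconcile the synopsis and Sections 5.2.5, 5.2.6.1 and 8.2.1 on two matters:

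1. The MTD is declared only at a level with 6 evaluable patients and at most 1 DLT. A level holding 3 is first filled to 6. The same applies to Cohort 0, and to 100 mg if it clears.
2. The text states what happens to accrual when the plan's own threshold of 2 DLTs is reached before a cohort is full.

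**Cost.** Some protocol wording, about 2.5 more escalation patients on average and about one more DLT window. The cap of 6 per cohort is unchanged, and five cohorts of 6 make the existing 30. One remote path would pass 30: Cohorts 1 to 4 all clear on 0/3, Cohort 5 fails, and each lower level then fails on filling, so that Cohort 0 opens (4 × 6 + 3 + 6 = 33, or 4 × 6 + 6 + 6 = 36). The probability that one level clears and then fails on filling is (1−p)³ × [3p²(1−p) + p³]. On the second curve the product over Cohorts 1 to 4 is 0.0204 × 0.0532 × 0.0774 × 0.0708, about 6 in a million. One sentence on how the cap of 30 applies there would settle it.
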